#### 12.4.4.5 *Examination of subgroups*

The subpopulation “nasolabial folds” will contain all subjects treated for nasolabial folds, regardless if they have been treated for one or both other indications as well. The subpopulation “marionette lines” will contain all subjects treated for marionette lines, regardless if they have been treated for only one or for two other indications as well. The subpopulation “cheek volume loss” will contain all subjects treated for cheek volume loss, regardless if they have been treated for one or both other indications as well. Each of these three subpopulations will contain approximately 175 subjects. Each subject will belong to at least two of these subpopulations. At least 50% of the subjects will be treated in all of the three indications and as consequence these subjects will belong to all of these three subpopulations (i.e., nasolabial folds, marionette lines, and cheek volume loss).

For the performance variables iGAIS, sGAIS, [REDACTED] [REDACTED] [REDACTED] for subject dispositions, demographic data, and for all safety analyses (analysis of TEAEs), subgroup analyses will be performed for each indication (subjects treated for nasolabial folds, for marionette lines and/or for cheek volume loss) in addition to the total population.

Responder analysis of MNLFS, MUCFS, and MMLS will only be performed for the subpopulations and not for the total population. [REDACTED] [REDACTED]

[REDACTED]  
[REDACTED]  
[REDACTED]  
[REDACTED]

 - confidential -	Merz Pharmaceuticals GmbH	M900391005/RaLido	
	Clinical Protocol for post market clinical follow-up studies (PMCF)		Version 1.0 18-Jun-2018

[REDACTED]

 - confidential -	Merz Pharmaceuticals GmbH	M900391005/RaLido
	Clinical Protocol for post market clinical follow-up studies (PMCF)	Version 1.0 18-Jun-2018

## 13 DATA HANDLING AND RECORDKEEPING

By signing and dating the eCRF, the investigator will confirm that all studies have been completed and conducted in compliance with the CP, and that reliable and complete data have been entered into the eCRF.

### 13.1 Corrections to data

All data required by this CP are to be recorded in the eCRF as soon as possible. However, direct entries are not allowed; data must be transcribed from the source documentation (e.g., subject file, scales) to the eCRF.

All data required by this CP are to be entered into a sponsor-validated database of eCRFs.

If corrections are necessary, an authorized member of the investigator's site staff will enter the correct data into the web-based eCRF. The audit trail in the electronic data capture system documents all changes.

The CRO's/sponsor's data management function will be responsible for data processing, in accordance with the CRO's/sponsor's data management procedures. Database close will occur only after quality assurance procedures have been completed.

### 13.2 Recordkeeping

Essential documents should be retained for a period of at least 10 years. Destruction of the documents after this period is only allowed after written agreement with the sponsor.

Essential documents at the study site include (among other documents):

- Source documentation (e.g., subject files, photos, scales).
- Subject identification code list (i.e., provided by template to the investigator, along with the ISF, at the beginning of the study), which identifies the subject by number, name, and date of birth.
- A signed copy of the final CP and any amendment.
- Investigator's compact disc/digital versatile disc with eCRF data, data clarification forms, and any associated subject-related source data (or, where applicable, authorized copies of source data).

 - confidential -	Merz Pharmaceuticals GmbH M900391005/RaLido	
	Clinical Protocol for post market clinical follow-up studies (PMCF)	Version 1.0 18-Jun-2018

- Signed informed consent forms.
- Copies of site investigators' and co-worker's curricula vitae.
- Copies of all direct correspondence with the EC (submission and approval letters).
- Copies of study supply receipt forms and device inventory forms.
- Copies of all essential correspondence between the investigator and the monitor, and between the investigator and the sponsor.
- Copies of safety information reported during the study and submitted by the sponsor.

### **13.3 Destruction of study documents**

Study documents may not be destroyed by study site personnel prior to the retention period specified above without the prior written consent of the sponsor. The study institution must inform the sponsor in due time if the principle investigator leaves the institution during the retention period. This rule also applies when the institution closes within the retention period.

 - confidential -	Merz Pharmaceuticals GmbH M900391005/RaLido	
	Clinical Protocol for post market clinical follow-up studies (PMCF)	Version 1.0 18-Jun-2018

## 14 PUBLICATION POLICY

The study results should be published in the public domain, and publishing details will be given in the clinical study agreement. Publications concerning study results must be approved in advance by the sponsor in writing.

The results of this study and any discoveries related to this study, regardless of whether they have technical or medical character, are the property of the sponsor.

The sponsor ensures that the study is registered, and study results are disclosed in at least one public clinical study registry, in accordance with national/international regulations and other requirements. Study registration may include a list of the study sites, as applicable.

 - confidential -	Merz Pharmaceuticals GmbH	M900391005/RaLido
	Clinical Protocol for post market clinical follow-up studies (PMCF)	Version 1.0 18-Jun-2018

1 LIST OF ABBREVIATIONS

AE	Adverse event
ATC	Anatomical Therapeutic Chemical classification system of the World Health Organization
CRF	Case report form
DRM	Data review meeting
FAS	Full analysis set
iGAIS	Investigator Global Aesthetic Improvement Scale
MedDRA	Medical Dictionary for Regulatory Activities
MMLS	Merz Marionette Lines Scale
MNLFS	Merz Nasolabial Folds Scale
MUCFS	Merz Upper Cheek Fullness Scale
n	Number of non-missing observations
PDF	Portable document format
PMCF	Post-market clinical follow-up
PPS	Per protocol set
PT	Preferred term
Q1	First quartile
Q3	Third quartile
SAE	Serious adverse event
SAP	Statistical analysis plan
SAS®	Statistical Analysis System software
SD	Standard deviation
SES	Safety evaluation set
sGAIS	Subject Global Aesthetic Improvement Scale
SMD	Study medical drug
SOC	System organ class
TC	Telephone contact
TFLs	Tables / figures / listings
TEAE	Treatment emergent adverse event
V	Visit
VAS	Visual Analogue Scale
WHO	World Health Organization

2 GENERAL AND TECHNICAL ASPECTS

The objective of this statistical analysis plan (SAP) is to specify the statistical analyses with appropriate detail and precision to serve as a guideline for statistical programming and creation of tables, figures, and listings for clinical study protocol M900391005, dated 18-Jun-2018.

All programs will be written using Statistical Analysis System Software (SAS[®]) version 9.4. A font size of 10 points with a unique font size for the whole document required will be used for the tables and figures in section 14, corresponding to a linesize of 111 digits and a pagesize of 42 lines for an output in A4 landscape format. For listings, a standard font size of 10 points with the linesize and pagesize as defined above will be used to produce the output in A4 format. Individual SAS programs will be written for all tables, figures, and listings. All outputs will be transferred into portable document format (PDF) files using the Merz internal SAS macro LST2PDF. These PDF files will be generated as needed to populate the subsections of Section 14 and Section 16.2 for the clinical study report. Each PDF file will include the corresponding table of contents, preceding the content of the file.

The Merz standard Table, Figures, and Listings (TFLs) for medical devices, version 1.0 will be applied and adapted to study specific requirements as laid down in the clinical study protocol and any amendments.

3 CLINICAL STUDY DESIGN AND OBJECTIVES

3.1 Clinical Study Design

This study is an open-label, multicenter, uncontrolled, post-market clinical follow-up (PMCF) study with a rater-blinded live evaluation. There will be no control group as the objective is to confirm safety and performance in “real-life”. Approximately 175 subjects per indication seeking for dermal filler/volumising treatment in the face, who agree to participate by signing the written informed consent form and who are fulfilling inclusion/exclusion criteria will be enrolled at approximately 15-20 sites.

Since subjects must be treated for at least two and up to three indications, selected out of nasolabial folds, marionette lines and cheek volume loss, and since it is planned to collect and analyze data from about 175 subjects per separate indication, about 210 subjects in total are planned to be enrolled.

Assuming that 50% of subjects will be treated for two and 50% for three indications respectively, at least 105 subjects will be treated in all of the three indications (i.e. nasolabial folds, marionette lines, and cheek volume) and 35 subjects will be treated in one of the possible treatment combinations:

- Nasolabial folds + marionette line;
- Nasolabial folds + cheek volume;
- Marionette lines + cheek volume.

If the number of subjects treated in all of the three indications is higher than 105, the number of subjects treated for only two indications may be reduced so that the total number of all treated subjects will be 210 but the aim to treat 175 subjects for each of the indications will be reached.

The duration of the study per subject is approximately 18 months (in case of no touch-up performed at Visit (V) 2) and 19 months (in case of touch-up performed at V2).

The study medical device (SMD) is CE-marked in Europe since 02-JUN-2016 and will be injected as per its current approved labelling and investigator's usual practice at Day 1 with an optional touch-up treatment after 4 weeks.

The subject will be injected at Day 1 with volume for each area to be treated, using injection techniques based on investigator's judgement, skin condition, safety and subject's expectations. A minimum of two and a maximum of three indications (nasolabial folds, marionette lines, cheeks) per subject can be treated. An optional touch-up can be performed after four weeks at V2 in the indications that were treated at Day 1, to obtain an optimal aesthetic outcome, as appropriate.

If the subject fulfills the inclusion criteria and agrees to participate, he/she will attend six visits (if no touch-up is performed), six visits plus one telephone contact (TC) (if touch-up is

CONFIDENTIAL

Page 7 of 31

Template: tem-sap-v5-20170522

File name: M900391005-sap-v1.0 Final-2019-07-30.docx

performed in all indications that were treated at Day 1), or seven visits plus one TC (if partial [i.e. in at least one, but not in all indications that were treated at Day 1] touch-up treatment is performed) in total. If any serious adverse event (SAE) related to the injection or the SMD is not resolved by the end of the study, the subject will be followed until the resolution of the SAE by the Merz Pharmaceuticals Department of Product Safety.

An interim analysis report is planned on 6 months data (Week 24/28 respectively, depending on touch-up).

Level and method of blinding

Assessments that will be used for the primary variable and some other variables will be performed by a blinded rater who is not otherwise involved in study procedures.

End of study

The end of study will be defined as the last visit of the last subject.

3.2 Clinical Study Objectives

Primary objective(s)

The primary objective of this PMCF study is to collect clinical data to confirm performance and safety for the injectable medical device RADIÉSSE® (+) Lidocaine, when used in accordance with its labelling in the treatment of nasolabial folds, marionette lines and/or cheek volume loss. The primary objective time point will be at Week 12/16 (depending on touch-up).

Secondary objective(s)

The secondary objective is to analyze performance at all objective time point(s) other than the primary ones.

4 DETERMINATION OF SAMPLE SIZE

The sample size estimation is based on the primary performance analyses, i.e., on three one-sided exact one-sample binomial tests (one test for each indication). Under the following assumptions 140 subjects are required per indication to reach a global power of 80%:

- Global significance level: 0.025 (one-sided)
- Local significance levels for tests per indication: $\alpha_1 = 0.0083$, $\alpha_2 = 0.0125$, $\alpha_3 = 0.025$ (Bonferroni Holm adjusted alpha)
- Proportion of responders under the null hypothesis 0.6
- Expected responder rate under test treatment: 0.75
- Power for each single test: 89.6% (for α_1), 92.6% (for α_2), 96.6% (for α_3)
- Global power for all tests under independence 80.1%

In order to have sufficient subjects for safety analysis the sample size is increased to 175 subjects per indication so that a minimum of 161 subjects per indication will complete the study. In 161 subjects per indication an adverse event (AE) with a true incidence of 1% will be observed at least once per indication with a probability of 80%. The total number of 210 subjects to be treated was chosen to have approximately 175 subjects treated per indication.

5 ANALYSIS SETS

The following analysis sets will be defined for the statistical analysis of this clinical study:

Safety Evaluation Set (SES)

The SES is the subset of all subjects who were exposed to the SMD at least once.

Full Analysis Set (FAS)

The FAS is the subset of subjects in the SES for whom at least one of the primary performance variables is available (i.e., all subjects who have a baseline and a post-baseline MAS value of at least one treated indication).

Per Protocol Set (PPS)

The PPS is the subset of subjects in the FAS without major protocol deviations whereby subjects with missing primary performance variable will be excluded from PPS. Major protocol deviations will be defined during the Data Review Meeting (DRM).

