### **Full Analysis Set [FAS]**

The FAS is the subset of subjects in the SES for whom at least one of the primary performance variables is available (i.e., all subjects who have a baseline and a post-baseline primary performance value of at least one treated indication).

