#### **12.4.4 Special statistical/analytical issues**

##### **12.4.4.1 Discontinuations and missing data**

Discontinued subjects will not be replaced.

For responder analyses missing values will be evaluated as non-responder (worst case replacement). [REDACTED]

[REDACTED]

[REDACTED]

[REDACTED]

[REDACTED]

[REDACTED]

[REDACTED] analyses except responder analysis [REDACTED] will be performed on observed cases only.

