7 STATISTICAL ANALYSIS METHODS

7.1 Performance Variables

All performance analyses will be based primarily on the FAS and additionally for primary performance analyses on the PPS. Where applicable, subgroup analyses will be performed on the following subpopulations “nasolabial folds”, “marionette lines” and “cheek volume loss”. Statistical tests will be one-sided hypothesis tests for responder rates. The Bonferroni Holm alpha correction will be used for three statistical testes to adhere to the global significance level of 0.025.

Continuous variables (values and changes from baseline) will be summarized by number of non-missing values (n), mean, standard deviation (SD), median, quartiles, minimum, and maximum. For qualitative variables, absolute and percent frequencies (n, %) will be displayed. The responder analyses the percentage will be based on the number of subjects in respective indication group. The percentage of all other analyses will be based on the number of observed values. Confidence limits and descriptive p-values will be given, where appropriate.

For performance variables the measurement at V1 (Day 1) is defined as baseline value.

P-values will be reported to four decimal places (e.g., p=0.0375). P-values below 0.0001 will be presented as ‘<0.0001’.

Mean, first quartile (Q1), median, and third quartile (Q3) will be reported to one decimal place more than the data were collected, for the standard deviation two decimal places more will be displayed; for derived data, an adequate number of decimal places will be chosen. Percentages will be calculated using the denominator of all subjects in a specified population and treatment group. The denominator will be specified in a footnote to the tables for clarification if necessary. Percentages will be reported to one decimal place.

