7.1.1 Primary Performance Variable(s)

For the primary performance analyses, responder rates for nasolabial folds, for cheek volume loss, and for marionette lines will be summarized as absolute and percent frequencies (n, %). The denominator for each response will be the number of subjects in the analysis set treated in the indication. Only the subjects of the FAS treated for the corresponding indication will be included into the analyses of responder rates. Any subject with missing assessment will be evaluated as non-responder in the FAS. Subjects with missing assessments with respect to the primary performance variables will be excluded from the PPS.

The aim of primary performance analyses is to show that there are:

- significantly more than 60% of responders in treatment of nasolabial folds

- significantly more than 60% of responders in treatment of marionette lines
- significantly more than 60% of responders in treatment of cheek volume loss

A confirmatory exact one-sample binomial test will be used to test probability of being a responder (p) is above 60% separately for each indication:

- $H_0 \text{ nasolabial folds: } p \leq 0.6$ vs. $H_1 \text{ nasolabial folds: } p > 0.6$
- $H_0 \text{ marionette lines: } p \leq 0.6$ vs. $H_1 \text{ marionette lines: } p > 0.6$
- $H_0 \text{ cheek volume loss: } p \leq 0.6$ vs. $H_1 \text{ cheek volume loss: } p > 0.6$

Using the Bonferroni Holm alpha correction with global significance level of 0.025 for the test with lowest p-value the local significance level α_1 is 0.0083. For the test with the second lowest p-value α_2 is 0.0125. For the test with the highest p-value α_3 is 0.025. If the lowest p-value of a single (one-sided) hypothesis is below 0.0083 it is shown that the responder rate lies significantly above 60% for this indication. In this case performance is shown for this indication. If additionally the second p-value of a single (one-sided) hypothesis is below 0.0125 it is shown that the responder rate lies significantly above 60% also for this indication. If additionally the highest p-values of the single sub-hypothesis are below 0.025, the primary objective regarding performance (i.e., performance shown for all three indications) can be concluded. The procedure is stopped if a p-value is higher than the corresponding local significance level. In this case no subsequent null hypothesis will be rejected.

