Point estimates of the rates will be provided with exact one-sided 97.5% Clopper-Pearson confidence intervals. The following SAS code will be used:

```
proc freq data = dataset order = freq;
  tables response / binomial (p=.6) exact cl alpha=.05;
  exact binomial;
run;
```

Confirmatory testing will be performed on the FAS with missing response imputed as non-responder. Furthermore, sensitivity analysis on PPS (observed case) will be performed.

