7.4 Special Statistical/Analytical Issues

7.4.1 Discontinuations and Missing Data

Discontinued subjects will not be replaced.

For responder analyses, missing values will be evaluated as non-responder (worst case replacement) for FAS. PPS will be used only for the primary performance analyses. Subjects with missing assessments with respect to the primary performance variables will be excluded from the PPS. Therefore no missing value replacement is needed for PPS.

Missing values for all further variables will not be imputed. All analyses except responder analysis [REDACTED] will be performed on observed cases only.

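### SAP 5 defines the full analysis set by two clauses that disagree, and a treated subject with no post-baseline rating is never counted as a non-responder (minor effect)

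*SAP*

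**What the plan says.** Protocol 12.2 and SAP 5 open the FAS definition in the same way: a subject from the safety evaluation set for whom one or more primary performance variables exist. Those variables are responses at Week 12/16 (protocol 12.3.1.1, SAP 6.1.1). Each document then explains the clause differently:

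- SAP 5: "all subjects who have a baseline and a post-baseline MAS value of at least one treated indication".
- Protocol 12.2: "all subjects who have a baseline and a post-baseline primary performance value of at least one treated indication".

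The rules that depend on this set are:

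- SAP 5 makes the per protocol set (PPS) a subset of the FAS and adds that "subjects with missing primary performance variable will be excluded from PPS".
- SAP 7.1.1: "Any subject with missing assessment will be evaluated as non-responder in the FAS", and "Confirmatory testing will be performed on the FAS with missing response imputed as non-responder".
- Protocol 12.4.1.1 and SAP 7.1.1 both admit to the responder analyses only FAS subjects treated for the indication concerned.

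The blinded rater scores the Merz Aesthetic Scales (MAS) at Week 4 (protocol 9.5, V2). Protocol Table 7 also requires a final study visit after premature discontinuation, and that visit includes a MAS rating. SAP 8 declares no change from the protocol.

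**The concern.** The two clauses in SAP 5 do not select the same subjects. Someone rated at Week 4 and then lost is in the FAS under the explanatory clause and counts as a non-responder. Under the lead clause the same person is outside the FAS and leaves both numerator and denominator. A programmer could follow either clause.

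A gap also remains on both readings. A treated subject with no post-baseline rating in any treated indication is in the safety set but not the FAS, so the non-responder rule never reaches that subject.

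The study has one arm and a fixed 60% bar. Leaving out an unrated subject, rather than counting that subject as a failure, raises the observed rate, and no control arm offsets it. The confirmatory denominator should be settled before the data are seen.

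**Working it through.** **1. The plan's own figure.** Inputs from SAP 4: n = 140 per indication, null rate 0.60, expected rate 0.75, Holm levels 0.025/3, 0.0125 and 0.025. For each level take the smallest r with P(X ≥ r | n, 0.60) ≤ alpha.

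- Critical counts: 99, 98, 96.
- Power at 0.75: 0.8962, 0.9261, 0.9656, matching the stated 89.6%, 92.6% and 96.6%.
- Product: 0.8015, matching the stated 80.1%.

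**2. Which reading fits the other rules.**

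- *Broad* (any post-baseline MAS value): subjects in the FAS can lack a Week 12/16 rating. The PPS exclusion and the imputation rule then both have work to do.
- *Narrow* (a Week 12/16 value is needed): imputation reaches only subjects rated at Week 12/16 in one treated indication but not in another.

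The broad reading is the more coherent one, but the SAP's lead clause contradicts it.

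**3. How many subjects could be affected.** The documents give no early dropout rate. Assumption: the margin in SAP 4, 175 − 161 = 14 per indication, is lost evenly over follow-up.

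- Broad, lost before Week 4: 14 × 4/72 = 0.78. With Binomial(175, 0.08 × 4/72): none 46%, one 36%, two or more 18%. Ratings at the final visit would lower this.
- Narrow, lost before Week 12/16: 14 × 12/72 = 2.3, or 14 × 16/76 = 2.9.

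**4. Critical counts at each Holm step (null 0.60).**

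| Unrated and excluded | n | Step 1 | Step 2 | Step 3 |
|---|---|---|---|---|
| 0 (all counted) | 175 | 121 | 120 | 119 |
| 1 | 174 | 121 | 120 | 118 |
| 2 | 173 | 120 | 119 | 117 |
| 3 | 172 | 119 | 118 | 117 |

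**5. When a conclusion changes.**

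- One missing, step 3: 118/174 gives p = 0.0203 and passes 0.025; 118/175 gives p = 0.0258 and fails. Steps 1 and 2 do not move.
- Two missing, step 1: 120/173 gives p = 0.0068 and passes 0.0083; 120/175 gives p = 0.0118 and fails.

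The chance that the decision differs is the chance of landing between the two critical counts. At 75% response among rated subjects:

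- One missing, step 3: 0.9869 − 0.9802 = 0.0067, about 0.7%.
- Two missing, step 1: 0.9617 − 0.9455 = 0.0162, 1.6%.
- Three missing, step 1: 0.9655 − 0.9307 = 0.0348, 3.5%.

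**6. Error rate if unrated subjects are true non-responders.** Set the all-treated rate at 60%, so the rate among rated subjects is 105/(175 − m) with m missing.

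| Missing | Step | Excluded | Counted |
|---|---|---|---|
| 1 | 1 | 0.0075 | 0.0075 |
| 1 | 2 | 0.0115 | 0.0115 |
| 1 | 3 | 0.0253 | 0.0172 |
| 2 | 1 | 0.0111 | 0.0072 |
| 3 | 1 | 0.0164 | 0.0070 |

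If missingness is unrelated to response, excluding one subject gives a step 3 error of 0.0203, within 0.025.

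**The case against.** The best defence is that the denominator is less open than it looks. A reader might infer two further conflicts:

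- Protocol 12.4.4.1 states the worst-case rule without naming a set, while SAP 7.4.1 restricts it to the FAS. That could look like an undeclared change.
- SAP 7.1 says "The responder analyses the percentage will be based on the number of subjects in respective indication group", which could look like a rival denominator of all treated subjects.

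The documents support neither. Protocol 12.4.1.1 already limits responder analyses to FAS subjects treated for the indication, and SAP 7.1.1 repeats this and takes its denominator from the analysis set. The SAP restriction is therefore not a change from the protocol, and SAP 8 is not wrong on that point.

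The protocol's explanatory clause can also be read as any post-baseline value on a primary scale, in which case the SAP wording clarifies it. That softens the difference between the documents. It does not remove the contradiction inside SAP 5 between its lead clause and its explanatory clause.

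Whether a never-rated subject is a failure is a choice of estimand, and both documents make it through the FAS. The even-loss assumption is not theirs: 161 is a completer target set for the safety analysis, not a dropout forecast. Both points stand. They limit the size of the finding and make the second part of the fix an improvement, not the correction of an error.

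**Conclusion.** The contradiction in SAP 5 is certain from the text. So is the gap for treated subjects with no post-baseline rating. The practical effect is minor.

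On the broad reading, which fits the plan best, 0 to 1 subjects per indication are affected under even loss. A conclusion then changes only at exactly 118 responders at the third Holm step, which is reached only after the other two indications have passed. The narrow reading raises the count to 2 to 3 and the first-step decision difference to 1.6% to 3.5%. Losses clustered before Week 4 would raise the broad-reading count.

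A reader might infer that dropouts in general escape the non-responder rule. On the broad reading they do not: a Week 4 or final-visit rating brings most of them into the FAS, where a missing Week 12/16 rating counts as failure. A reader might also infer that the type I error is inflated. The excess (0.0253 against 0.0172 at step 3 with one missing) appears only if unrated subjects are assumed to be true non-responders.

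**What to change.** 1. **SAP 5:** delete the lead clause, so that the FAS is safety-set subjects with a baseline and any post-baseline MAS value in at least one treated indication. This alone resolves the contradiction.
2. **SAP 7.1.1, a cheap improvement:** for each indication, make the confirmatory denominator all subjects treated in that indication with a Day 1 MAS. Count any missing Week 12/16 rating as non-response, including where there is no post-baseline rating at all.
3. Record both as changes in SAP 8 before the first database close (protocol 11.3). Align protocol 12.2, 12.4.1 and 12.4.1.1, because item 2 departs from the rule that only FAS subjects enter the responder analyses.

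**Cost.** Wording, one programming flag, and a footnote where the confirmatory denominator exceeds the FAS count. No new data are needed. Each added subject lowers the observed rate by about 0.4 points: 130/174 = 74.7% against 130/175 = 74.3%.

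Power for all three indications, by the SAP's own product of single-test powers, with 75% among rated subjects and unrated subjects counted as failures:

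- 1 missing: 0.9577 × 0.9707 × 0.9802 = 91.1%.
- 2 missing: 0.9455 × 0.9617 × 0.9737 = 88.5%.
- 3 missing: 0.9307 × 0.9505 × 0.9655 = 85.4%.

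All stay above the planned 80%.
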